### Hierarchical model

Generalized Linear Model will be used to fit a Poisson regression of daily AF episodes against temporal variables and DDS data based in hierarchical model. Data model with random effect include repeated episodes of AF in each patien, the intervention groups and the 3 sites of the research. Date model with fixed effect include DDS event during the period of the study.

Analysis will be performed using R Project for Statistical Computing version 3.0 or higher and IBM SPSS software version 23 or higher.

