# **Study Population**

Study population, sample size and location: Men and women with prior implantation of a dual lead (atrial and ventricular) pacemaker or ICD, will be recruited from cardiac arrhythmia clinics in General Hospital in Nicosia-Cyprus (n=156) in project years 2018-2019 and 2019-2020. Recruitment of participants will be facilitated through the network of physicians in Nicosia General Hospital. In order to facilitate recruitment, relations will be established with the Administrative and Nursing staff of the Clinics and Patients' Associations and the details of the project will be explained to them. During fall 2018 and 2019, MEDEA personnel will start recruitment efforts to detect eligible AF patients for participation in the study in the high DDS periods of February-May 2019 and 2020.

The same number of patients will be recruited in each study site (Beer Sheba, Heraklion, Nicosia) and we expect that a total of 468 AF patients will be recruited. We estimate a dropout rate of 30%, which will eventually give us 324 AF patients to analyse. The feasibility of protocols to assess health outcomes in vulnerable patient groups will be tested in the pilot study during the high DDS outbreaks season of 2018 with and without implementation of exposure reduction guidelines in all study sites in a small number of patients (6 AF patients per study site).

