# 3.2 Study Rationale

#### Desert dust storm events across Southern Europe

A dust storm is a phenomenon common to arid and semi-arid regions. In the EU, the term "Desert Dust Storms (DDS)" is used in the context of sandstorms originating primarily from the Sahara desert but also from the Arabian–Negev desert. The term DDS refers to the condition created when finer sand particulate matter (PM) from the desert surface is transported over a long distance. DDS pose a major risk to populations residing in affected areas, such as in Mediterranean countries belonging to the global dust belt, extending from West Africa to the Arabian Peninsula (Querol et al., 2009). During DDS events, which can last for several days,  $PM_{10}$  levels are considerably higher than the 2005 EU daily limit value of 50 µg/m^3 (Achilleos et al, 2014). Dust PM is mostly composed of rock-forming and clay minerals and they may carry microbial agents, such as bacteria, fungi and viruses (Griffin et al, 2007), and mix with anthropogenic atmospheric pollutants during transport.

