# 4 STUDY DESIGN

Type of study: Randomized clinical trial (Behavioural Intervention)

Patients with AF will be recruited during DDS outbreaks and will be randomized into three parallel groups to receive:

- a) No intervention for DDS,
- b) Intervention for outdoor exposure reduction, and
- c) Interventions for both outdoor and indoor exposure reduction.

Disease-related adverse health outcomes will be assessed in all the parallel arms of the study.

Previous publications of the MEDEA partners (Achilleos et al, 2014; Gerasopoulos et al, 2006; Krasnov et al, 2014), indicated that 2/3 of each year's DDS events in the Eastern Mediterranean region appear during February-May, with 10-15% of the days during this period being "DDS days". Thus we will perform this public health intervention study during February–May of 2019 and 2020.

Study population and location: Men and women with prior implantation of a dual lead (atrial and ventricular) pacemaker or ICD, will be recruited from the cardiac arrhythmia clinic at the Nicosia General Hospital of Cyprus (n=156) in project years 2018-2019 and 2019-2020. Each patient will have assessment of health outcomes during only one high DDS period.

Duration of the study: A feasibility trial and refinement of protocols and tools will be performed in the high DDS period of 2018. In the fall of 2018 and 2019, MEDEA personnel will start recruitment efforts to detect eligible AF patients for participation in the study during the high DDS periods of February-May 2019 and 2020.

Assessment of health outcomes:

- The occurrence of AF/ventricular arrhythmia episodes will be recorded daily using the already implanted participants' pacemakers or ICD during the 4-month study period. The recorded episodes will be downloaded with interrogation of the pacemaker or ICD during a visit to the Arrhythmia Clinic after the end of the study period.
- Phone interviews every 1 month throughout the high DDS outbreaks season will be carried out. Data collected will include symptoms of fatigue, change in medication use and unscheduled visits to health professionals for heart arrhythmias/episodes.
- Continuous recordings of biological parameters (pulse rate, pulse rate variability and temperature) obtained by wearing smart watch sensors and uploaded on line to the secure e-platform.

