Summaries of main variables will be presented in form of means and standard deviations for normal distributed quantitative variables, medians and ranges for non-normal distributed quantitative variables, distribution in percentages for qualitative variables.

Univariate analysis

Univariate analysis will be mostly used for analysis initial datasets consisted of personal data records.

The method of analyses for continuous variables will be parametric using Paired and Unpaired t-test and Repeated Measurements ANOVA.

Non-parametric procedures will be used if parametric assumptions could not be satisfied, even after data transformation attempts. These tests will include Mann-Whitney, Wilcoxon and Spearman Correlation tests.

Categorical variables will be tested using Chi-Square test.

Multivariate analysis

We will apply 2 modelling strategies:

Case- Crossover design

The association between DDS events and episodes of cardiac arrhythmia will be assessed in a casecrossover design ⁽¹⁰⁾. This method has been used previously to study triggers of acute cardiovascular events ⁽¹¹⁾. We will define case periods by the time of each confirmed episode of cardiac arrhythmia, rounded to the nearest hour. We will match control periods on weekday and hour of the day within the same calendar month. Conditional logistic regression analysis will be performed to analyze the exposure odds ratio with 95% confidence intervals on risk of cardiac arrhythmia.

Hierarchical model

Generalized Linear Model will be used to fit a Poisson regression of daily AF episodes against temporal variables and DDS data based in hierarchical model. Data model with random effect include repeated episodes of AF in each patient, the intervention groups and the 3 sites of the research. Date model with fixed effect include DDS event during the period of the study.

Analysis will be performed using R Project for Statistical Computing version 3.0 or higher and IBM SPSS software version 23 or higher.

3. References

Voorend-van Bergen S, et al. Monitoring childhood asthma: web-based diaries and the asthma control test. J Allergy Clin Immunol. 2014;133:1599-605.

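### Beyond patient, group and site random effects, the Poisson model of daily AF episodes has no term for residual overdispersion, serial correlation or shared site-day variation, so its dust-effect intervals may be too narrow.

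*Protocol*

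**What the plan says.** Protocol section 8.2.3 (Hierarchical model) and the SAP section of the same name describe one model: "Generalized Linear Model will be used to fit a Poisson regression of daily AF episodes against temporal variables and DDS data". The next sentence lists the random effects, in the SAP's wording "Data model with random effect include repeated episodes of AF in each patient, the intervention groups and the 3 sites of the research"; the protocol's version differs only by a typing slip. The fixed part is given as "Date model with fixed effect include DDS event during the period of the study". The temporal variables are not listed.

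Neither document names a dispersion parameter, a negative binomial or quasi-Poisson alternative, a day-level or site-day random term, an autoregressive structure, a robust variance, or a check for overdispersion.

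Three design facts bear on this. Episodes are "recorded daily using the already implanted participants' pacemakers or ICD during the 4-month study period" (protocol section 4). The same section has "10-15% of the days during this period being" dust days. Section 3.2 describes how PM10 rises "During DDS events, which can last for several days".

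**The concern.** A patient random intercept describes how patients differ on average. It says nothing about how one patient's count varies from one day to the next. The dust coefficient is estimated almost entirely from that day-to-day variation, because a patient's dust days are compared with the same patient's other days.

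Two features make the assumption risky here. Dust days come in runs, so positive correlation between adjacent days adds to the variance of the dust contrast. Dust days are also common to all patients at a site, so anything else that moves those patients together on a day (weather, co-pollutants) does not average out over patients.

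At stake is the credibility of any dust effect reported from this model. Quantifying vulnerability during dust outbreaks is the first part of the primary objective in protocol section 2.1, and this is one of the two multivariate strategies listed.

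**Working it through.** The plan states no power, precision or error rate for this model, so there is no figure to reproduce. The 81% power concerns a different comparison.

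**Inputs from the documents.** 324 analysed patients ("which will eventually give us 324 AF patients to analyse"); three sites and two seasons; four months, taken as 120 days; 10-15% dust days, taken as 12.5%.

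**Assumptions.** 324/6 = 54 patients per site-season; dust in 3-day runs; mean 0.3 episodes per day (range 0.1 to 1); lognormal patient effects, log-SD 1; true dust effect zero. The dispersion and correlation values are also assumed.

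**Step 1: the model's own standard error.** Expected episodes = 324 × 120 × 0.3 = 11,664. With dust share p = 0.125, the information on the log rate ratio is 11,664 × 0.125 × 0.875 = 1,276, so SE = 1/√1,276 = 0.028. The simulated mean model SE was 0.0277.

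**Step 2: independent extra variation within a patient.** With negative binomial shape k, a count's variance is μ + μ²/k. The variance of the dust estimate is then inflated by 1 + (E[μ²]/E[μ])/k. For lognormal patient means, E[μ²]/E[μ] = 0.3 × e¹ = 0.815. With k = 1, √1.815 = 1.35 (simulated 1.30). With k = 0.3, √(1 + 0.815/0.3) = 1.93 (simulated 1.86).

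**Step 3: shocks shared by a site on a day.** The expected site-day total is 54 × 0.3 = 16.2. An independent shock of log-SD 0.2 adds 16.2 × (e^0.04 − 1) = 0.66 to the variance ratio. With lag-1 correlation 0.5 and 3-day runs, 0.66 is multiplied by about 1 + 2(2/3 × 0.5 + 1/3 × 0.25) = 1.83. The SE ratio is √(1 + 0.66 × 1.83) = 1.49 (simulated 1.45). The ordinary within-patient dispersion statistic in that simulation was 1.01, so it would not reveal the problem.

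**Step 4: simulation.** There were 400 replicates per setting. The estimator conditioned on patient totals, which stands in for a patient intercept. False positives are 100% minus coverage.

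| Residual variation assumed | Episodes/day | Actual SD ÷ model SE | 95% CI coverage | False positives |
|---|---|---|---|---|
| None; patient log-SD 1 | 0.3 | 0.94 | 97.5% | 2.5% |
| None; patient log-SD 1.5 | 0.3 | 0.98 | 95.2% | 4.8% |
| Day-level, k = 1 | 0.1 | 1.12 | 91.5% | 8.5% |
| Day-level, k = 1 | 0.3 | 1.30 | 86.8% | 13.2% |
| Day-level, k = 1 | 1 | 1.86 | 70.2% | 29.8% |
| Day-level, k = 0.3 | 0.3 | 1.86 | 68.5% | 31.5% |
| Patient AR(1), log-SD 0.7, correlation 0.5 | 0.3 | 1.40 | 83.8% | 16.2% |
| Patient AR(1), log-SD 1, correlation 0.7 | 0.1 | 1.33 | 88.2% | 11.8% |
| Patient AR(1), log-SD 1, correlation 0.7 | 0.3 | 1.72 | 74.8% | 25.2% |
| Patient AR(1), log-SD 1, correlation 0.7 | 1 | 3.12 | 50.7% | 49.3% |
| Patient AR(1), log-SD 1, correlation 0.9 | 0.3 | 1.99 | 69.0% | 31.0% |
| Site-day shock, log-SD 0.1, correlation 0.5 | 0.3 | 1.11 | 91.8% | 8.2% |
| Site-day shock, log-SD 0.2, correlation 0.5 | 0.3 | 1.45 | 82.5% | 17.5% |

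Monte Carlo error is about √(0.05 × 0.95/400) = 1.1 points near 5% and √(0.4 × 0.6/400) = 2.4 points near 40%.

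**Step 5: does clustering by patient repair it?** With k = 1 and lag-1 correlation 0.5, the plain Poisson test rejected a true null in 9%, 20% and 39% of trials at 0.1, 0.3 and 1 episode per day. Patient-clustered standard errors gave 5%, 5% and 6%. A separate run gave 22% and 38% at 0.3 and 1 per day, against 4-5% with patient clustering. With site-day shocks of log-SD 0.2 at 0.3 per day, the plain test rejected in 18.5% and the patient-clustered test in 19%. At log-SD 0.3 the figures were 28% and 27%; at 0.1 both were about 8%. Patient clustering gives no protection against shared shocks.

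**The case against.** A reader might infer that the model allows no overdispersion or day-to-day correlation at all. That goes too far. A patient random effect makes counts overdispersed across the whole sample and gives all of a patient's days an equal correlation. If that is the only heterogeneity, the first two table rows show no undercoverage.

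A reader might also infer that the intervals will certainly be too narrow. The documents do not support that: they give no episode rate, dispersion or autocorrelation. That AF episodes come in bursts is plausible, but it is an assumption. The undefined temporal variables could absorb some season or weather, though nothing suggests that they would absorb bursts within a patient.

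The plan also estimates the dust association by case-crossover, which does not use the Poisson variance. This is a partial safeguard only. Each confirmed episode is a case there, and no clustering by patient is named.

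Finally, the primary comparison is AF burden in the combined intervention groups against control. This model counts episodes and does not feed that comparison. Nor does the plan specify a dust-by-arm term, so nothing can be said about false positives for one. These limits on certainty and scope stand. The gap in the model's variance structure remains.

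**Conclusion.** The point holds as a risk to the supporting dust-association analysis. If only patients differ, false positives stay near 5%. With k = 1 and lag-1 correlation 0.5 they run from roughly 10% to 40% over 0.1 to 1 episode per day, and the wider grid of residual structures spans about 8% to 49%.

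As an illustration at 0.3 per day, for an estimated rate ratio of 1 the model would report a 95% interval of exp(±1.96 × 0.0277), or 0.95 to 1.06. With patient AR(1) variation (log-SD 1, correlation 0.7) the honest interval is exp(±1.96 × 0.0478), or 0.91 to 1.10.

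All of this rests on assumed rates, dispersion, correlation and run length. The documents do not support reading it as a flaw in the primary AF-burden result. It should be corrected before analysis.

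**What to change.** Amend the hierarchical-model text in both documents in one of two ways.

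- Replace the plain Poisson by a negative binomial mixed model, or a Poisson model with a patient-day random term, adding an AR(1) structure within patient and a site-by-day random effect.
- Keep the Poisson mean model and base all dust-effect intervals on a variance that respects both patient and site-day clustering, for example two-way clustering or a block bootstrap over days within site. Blocks of consecutive days should be long enough to cover a dust event and should keep all patients at the site together.

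Prespecify and report a dispersion check and a residual autocorrelation check. Apply both to site-day totals as well as to patients, because shared shocks barely show in the patient-level statistic.

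The cost is a few lines of SAP text, some extra programming and somewhat wider intervals, by the factors above if the extra variation exists and hardly at all if it does not. Dust events are few: 15 dust days in 3-day runs is about 5 events per site-season, or 30 over six. Any cluster-based variance should therefore carry a small-sample correction. The combined patient and site-day remedy was not itself simulated here and should be tested on simulated data before it is fixed.

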## 9 ASSESSMENTS OF ADVERSE EVENTS

Since, the intervention under study is behavioral/lifestyle intervention, it does not involve any specific drug administration nor any change in ongoing medication schedule. Furthermore, it does not include any invasive procedure and all the health outcomes are assessed using non-invasive methods (smart-watches, phone interviews) and questionnaires. Hence, there are no specific safety parameters to quantify adverse health events related to interventions.

At any point during the study, patients will have the opportunity to bring any evolving information or issue (e.g. health issue) that concerns them to the attention of the primary investigator, [name], whose contact information will be given to all

participants during the enrollment phase, and will also be available on the program's website.

## 10 INTERVENTION DISCONTINUATION

Subjects may withdraw voluntarily from the study at any time and for any reason.

Patients can make oral complaints to members of the research team as well as to the principal investigators of each site.

The criteria for intervention discontinuation will be:

- Non-adherence to the intervention
- Moving to a different house than the reported initial one
- Significant change in health status

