# 2.2 Secondary Objectives

The secondary objectives of the study are to:

- 1. Demonstrate which of the recommendations are effective in reducing outdoor and indoor exposures to DDS in a panel of adults with atrial fibrillation (AF)
- 2. Secondary health outcomes will be the occurrence of ventricular arrhythmias assessed through the pacemaker and heart rate variability.

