## 6.3 Adherence Assessment

The compliance to exposure-reduction guidelines will be monitored with the use of remote sensors. The intervention for outdoor exposure reduction, (by reducing the time spend outdoors and by avoiding physical activity) will be assessed with the use of smart wristwatches that will have global position system (GPS) and accelerometer. The intervention for indoor exposure reduction (by minimizing home ventilation and by filtering indoor air) will be assessed with the use of particle samplers that will be placed outside and inside houses.

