# 7 STUDY PROCEDURES

# 7.1 Schedule of Evaluations

Assessment	Baseline	Every 1 month ± 3 days.	4 months ± 30 days
Informed Consent Form	X		
Inclusion/Exclusion Criteria	Х		
Demographics	X	X	
Medical History	X	X	
House assessment		X	
Current Medications	Х	X	X
Intervention Discontinuation		X	X
Tel Questionnaire		X	
Daily recordings of AF/ventricular arrhythmia episodes			X
Continuous recordings of biological parameters (pulse rate, pulse rate variability, temperature)		x	X
Adverse Events		X	X

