#### Randomization

Following the eligibility assessment, participants will be randomized using PASS 14 software that allows for random number generation. Randomization will be carried out with a 1:1:1 ratio to three parallel groups:

- a) Control group A: No intervention for DDS,
- b) Intervention group B: Intervention for outdoor exposure reduction, and
- c) Intervention group C: Intervention for outdoor and indoor exposure reduction (patient's household/bedroom settings)
- 7.2.3 Follow-up Assessments
  - Intervention mid-point assessment April 2019/2020:
    - Current medications
    - Intervention discontinuation
    - Telephone questionnaire
    - Daily recordings of AF/ventricular arrhythmia episodes
    - Continuous recordings of biological parameters (pulse rate, pulse rate variability, temperature)
    - Adverse events

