#### 7.2.4 Completion/Final Evaluation

- Intervention end-point assessment May 2019/2020:
  - Current medications
  - Intervention discontinuation
  - Telephone questionnaire
  - Daily recordings of AF/ventricular arrhythmia episodes
  - Continuous recordings of biological parameters (pulse rate, pulse rate variability, temperature)
  - o Adverse events

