In our power calculations for the panel studies in asthmatic children and AF patients, the sample size included a dropout rate of 30%, which is an overestimation of the dropout rate observed in previous studies in Cyprus and countries of the region (15-20%). Thus, even if DDS events are 20-30% less we will have ample statistical power to detect a significant effect of each intervention.

2. Data Analyses

Analyses of health outcomes in asthmatic children

Our main outcome for the asthmatic children is the mean monthly change in ACT score. We will have 5 repeated measurements of ACT score per year for each participant and we can assess the effectiveness of each intervention to reduce asthma symptoms during DDS events.

Secondary outcomes will be repeated assessments of asthma medication use, unscheduled visits for asthma, forced expiratory volume in 1 second, peak expiratory flow, and FeNO. For the lung function parameters we will obtain at least three repeated observations for each subject within each group, and this will make possible to assess the health benefits of the intervention and attribute them to the assigned intervention.

Toward this end, we will apply the following regression mixed effects model:

EQUATION1

$$\begin{split} H_{ij} &= (\beta_o + \nu_{oi} + h_{oi}) + (\beta_1 + \nu_{1,i} + h_{1i}) * (T_{ij} + (1 - T_{ij}) SR_{ij}) * C_{ij} + \\ &\qquad (\beta_2 + \nu_{2i} + h_{2i}) * D_{ij} + \beta_3 * Temperature_{ij} \\ &\qquad + \sum_{m=1}^{M} \gamma_{1m} X_{1mi} + \sum_{n=1}^{N} \gamma_{2n} X_{2nj} + \sum_{p=1}^{P} \gamma_{3p} X_{3pij} + \epsilon_{ij} \\ &\qquad (\nu_{oj} \nu_{tj} \nu_{si} \nu_{di}) \sim [(0 \ 0 \ 0 \ 0), \sigma] \\ &\qquad (h_{oi}, h_{ti}, h_{si}, h_{di}) \sim [(0 \ 0 \ 0 \ 0), \sigma_{\Box}] \end{split}$$

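### Section 10 makes non-adherence a reason to discontinue the intervention, a rule that can act only in groups B and C and that either weakens the strategy tested or loses patients from one side

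*Protocol*

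**What the plan says.** Protocol section 10 first allows voluntary withdrawal from the study. It then lists three criteria for discontinuing the intervention: "Non-adherence to the intervention", a change of home, and a significant change in health. It gives no threshold for non-adherence, no assessor and no consequence.

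The related text is as follows.

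- **Who has an intervention.** Group A has none (section 7.2.2). Groups B and C receive smartphone alerts and instructions. C adds home measures and an air cleaner (section 6.2).
- **How adherence is seen.** Section 6.3 states: "The compliance to exposure-reduction guidelines will be monitored with the use of remote sensors". These are watches with GPS and accelerometer, and particle samplers at the home. The SAP, under the AF analyses, says that indoor and outdoor exposure data come from a random subgroup of 20 households per site. The planned recruitment is 156 patients per site.
- **What is to be learned.** Secondary objective 1 (section 2.2) is to "Demonstrate which of the recommendations are effective in reducing outdoor and indoor exposures to DDS".
- **When discontinuation is assessed.** "Intervention Discontinuation" is marked monthly and at four months in section 7.1. It appears again under "Intervention mid-point assessment April 2019/2020" (section 7.2.3) and "Intervention end-point assessment May 2019/2020" (section 7.2.4).

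Neither document says whether a discontinued patient stays in follow-up, and neither names an analysis set. Nothing elsewhere limits or reverses the criterion.

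**The concern.** The rule is one-sided, acts after randomisation, and is triggered by uptake of the advice, which the trial is meant to study. Section 3.2 of the protocol says the aim is evidence on recommendations that authorities already issue to the public. Public advice is not withdrawn from people who ignore it. A patient who ignores one storm warning may follow the next, and one who follows it in part may still benefit.

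What is at stake depends on what discontinuation means in practice:

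- **Alerts and advice stop, follow-up continues.** The B and C arms receive less of the intervention than the strategy of interest, and the contrast with A is diluted.
- **The patient leaves follow-up or analysis.** Patients are lost from B and C because of their behaviour, with no matching loss from A. If those lost have higher AF burden, the observed benefit is inflated.

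**Working it through.** **Inputs from the documents.** Analysed groups of 108 (A) and 216 (B+C); two-sided Mann-Whitney test at 0.05; Weibull with mean 15, SD 15 in control and mean 12, SD 15 under intervention (SAP section 1), so an effect of 3.0 points; recruitment of 468. Section 4 of the protocol describes February-May "with 10-15% of the days during this period being" dust days.

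**The plan's own figure.** The stated power is 81%. Simulating the SAP inputs gave 76.0% to 77.3% over several runs, so 81% was not reproduced. That is a separate matter. About 76% is used here as the starting value.

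**Dust days affected.** The season is 120 days, so 10-15% gives 12-18 dust days. If they are evenly spread (assumed), the days left after a stop are:

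- after 1 month: 9-13.5
- after 2 months: 6-9
- after 3 months: 3-4.5

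**Reading 1: alerts stop, follow-up continues.** None of the next three quantities is in the documents. Let q be the share of B+C stopped, p the share of the full effect a non-adherer would keep if alerts continued, and t the months before the stop. Take 3.0 points as the effect in adherers.

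- Effect with alerts continued: 3.0 × (1 − q + qp)
- Effect with the rule: 3.0 × (1 − q + qp × t/4)

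For q = 0.20 and p = 0.50, with 20,000 simulated trials per row (standard error about 0.3 points):

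| Case | Multiplier | Effect (points) | Loss from the rule | Power |
|---|---|---|---|---|
| No non-adherence | 1.000 | 3.000 | – | 76.0% |
| Alerts continued | 0.900 | 2.700 | – | 66.2% |
| Stop after 3 months | 0.875 | 2.625 | 2.8% | 64.6% |
| Stop after 2 months | 0.850 | 2.550 | 5.6% | 61.5% |
| Stop after 1 month | 0.825 | 2.475 | 8.3% | 59.2% |

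A repeat simulation gave 76.3%, 66.8%, 64.2%, 61.8% and 58.8% for the same rows. The fall from 76.0% to 66.2% is due to non-adherence itself. Only the further fall below 66.2%, which is 1.6 to 7.0 points, is due to the rule.

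The ends of the assumed range:

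- q = 0.10, p = 0.25, t = 3: multiplier 0.925 continued and 0.919 stopped, a loss of 0.7%. Power is 69.3% against 69.1%, which is within simulation error.
- q = 0.30, p = 0.50, t = 1: multiplier 0.850 continued and 0.7375 stopped, a loss of 13.2%. Power is 61.3% against 49.5%, a loss of 11.8 points.
- p = 0, or stopping only at the May assessment: no loss.

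**With lower dropout.** The SAP says "the sample size included a dropout rate of 30%, which is an overestimation of the dropout rate observed in previous studies" and puts the latter at 15-20%. Of 468 patients, 374 to 398 would then be analysed. With q = 0.20 and p = 0.50, power at 125 vs 249 is 73.5% with alerts continued, 70.8% with a stop at 3 months and 65.6% at 1 month. At 132 vs 265 it is 76.0%, 73.7% and 67.7%. The margin raises power with and without the rule and does not remove the difference.

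**Reading 2: stopped patients leave follow-up or analysis.** Suppose there is no true effect and the overall mean is 15. Assume a share f of B+C is lost and that those lost have mean burden d points above those who stay. The mean of those who stay is 15 − f × d. With f = 0.20 and d = 3 it is 15 − 0.6 = 14.4. That is a spurious benefit of 0.6 points, a fifth of the planned 3.0. In 10,000 simulated trials with 108 vs 173 (216 − 43), the two-sided rejection rate was 7.7% instead of 5%. If those lost had lower burden, the bias would run the other way.

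**The case against.** The strongest reply is that no passage says alerts stop. Section 6.2 sends alerts and instructions to B and C with no adherence condition. The visit schedules list discontinuation beside medications and adverse events, so section 10 may only define when a patient is recorded as discontinued. It could also concern leaving the study: it opens with study withdrawal, and moving house would not prevent smartphone advice to group B. This stands as far as it goes: the meaning is open, and the direction of any distortion depends on it. It does not rescue the criterion. Either operative reading acts on B and C alone, and if it is only a recording definition, the scheduled record in section 7.1 serves that purpose without it.

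The second reply also stands: every driver of the size is assumed. A patient non-adherent enough to be stopped may have little effect left to lose, and at the mild end the rule makes no detectable difference.

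Third, samplers cover only 20 households per site, so adherence to the indoor measures could not be judged from samplers in most of the 156 patients. Non-adherence would mostly be judged from the watches, which narrows the rule's reach without removing it.

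**Conclusion.** The point holds as a mismatch between a stated rule and the trial's question, and the criterion should be removed. The rule selects on post-randomisation behaviour in B and C only, and neither document fixes what follows. Under reading 1, with 10-30% stopped, 25-50% of the effect kept and a stop after one to three months, the loss is under 1 to about 12 points of power, and it can be nil. Under reading 2 the effect could be inflated, by 0.6 points in the illustration. Confidence in the size is low because the documents supply none of these inputs.

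Four stronger inferences are not supported:

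- **That the rule certainly withdraws advice, or certainly excludes patients from analysis.** The text says neither.
- **That the effect under the rule can only be equal or smaller.** That presumes alerts stop, follow-up continues, and continued advice never does harm, and the documents establish none of these.
- **That the rule costs the whole fall in power.** Setting the effect to zero in 10%, 20% or 30% of B+C gives about 67-68%, 57.5% and 46%, but this compares stopped patients with full effect in everyone. It is an upper bound that includes non-adherence itself.
- **That the rule removes the patients whose AF responds least.** The criterion concerns acting on the advice, not AF response.

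**What to change.** In Protocol section 10, delete "Non-adherence to the intervention" and leave the change-of-home and health-status criteria as they are. Add that:

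- alerts and guidance continue to all B and C patients whatever their measured adherence;
- pacemaker data are downloaded for every randomised patient;
- patients are analysed in the group to which they were randomised.

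State the last item in the SAP as well. Report adherence as a result under secondary objective 1, noting that sampler data cover only the household subgroup. Keep the scheduled discontinuation record in section 7.1.

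The cost is one deleted criterion and a few sentences. The e-platform is already planned for sending the alerts, and a device interrogation after the monitoring period is already planned. The downside is that messages continue to some patients who ignore them, who may still withdraw. The change does not cure the dilution caused by non-adherence itself.
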